7.3.1 Primary Efficacy Analyses

The primary efficacy analyses will be performed for month 6 visit using the ITT population. The null hypothesis for the primary efficacy variable, complete overall ocular discomfort response, is that 0.1% AGN-195263 is no different than vehicle with respect to the proportion of patients who are complete overall ocular discomfort responders at month 6. The alternative hypothesis is that a between-group difference exists. As described above, patients who discontinued from the study due to lack of efficacy or used SAT or other prohibited treatments within the impact intervals specified will be counted as non-responders in the analysis. Missing data due to other reasons including intermittent missing visits, early discontinuation due to reasons other than lack of efficacy will be imputed by the LOCF method. The achievement of complete overall ocular discomfort response will be determined including the imputed data. The null hypothesis will be tested using the CMH method stratified by gender and baseline overall ocular discomfort score (1 vs 2 to 3). The between-group difference in the responder rate will be reported with the confidence intervals estimated based on the normal approximation for the binary variable.

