The primary efficacy variable is the complete overall ocular discomfort response at month 6. A patient will be considered to be a complete ocular discomfort responder if the overall ocular discomfort score is 0 at month 6. The between-group difference in the proportion of responders will be analyzed using the CMH method stratified by gender and baseline overall ocular discomfort score (1 vs 2 to 3).

The secondary efficacy variables include change from baseline in TBUT, complete blurred vision response, complete corneal sodium fluorescein staining response, complete ocular burning response, change from baseline in overall ocular discomfort score, at least 1 grade improvement in overall ocular discomfort score, at least 2-grade improvement in overall ocular discomfort score, and at least 50% improvement in overall ocular discomfort score. For each of blurred vision, corneal sodium fluorescein staining, and ocular burning, a complete responder is a patient with a score of 0. The continuous secondary efficacy variable, change from baseline in TBUT, will be analyzed using an analysis of covariance (ANCOVA) model with treatment, gender, baseline overall ocular discomfort score (1 vs 2 to 3) as factors and baseline TBUT as a covariate. The dichotomous secondary efficacy variables (complete blurred vision response, complete corneal staining response, and complete ocular burning response) will be analyzed using the CMH method stratified by gender and baseline value (1 vs 2 to 3) of the corresponding variable. Other dichotomous secondary efficacy variables derived from the overall ocular discomfort score at month 6 (ie, \geq 1 grade improvement from baseline, \geq 2-grade improvement from baseline, and \geq 50% grade improvement from baseline) will be analyzed using the CMH method stratified by gender and baseline overall ocular discomfort score (1 vs 2 to 3). The change from baseline in overall ocular discomfort will be analyzed by an ANCOVA model with treatment and gender as factors and baseline overall ocular discomfort score as a covariate.

[figure not shown]
Safety:

[figure not shown]

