5.4 Treatment Allocation Ratio and Stratification

At the time of randomization (baseline, day 1), patients will be randomly assigned in a 1:1 ratio to receive either 0.1% AGN-195263 [REDACTED] or its vehicle

during the randomized study treatment phase. Patients will be stratified by gender and baseline (day 1) overall ocular discomfort score (1 vs 2 to 3). There will be 4 stratification groups as shown in Table 5.

Table 5 Stratification Groups

Stratification Group	Gender	Baseline Overall Ocular Discomfort Score
1	Male	1
2	Male	2 to 3
3	Female	1
4	Female	2 to 3

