6.5 Summary of Methods of Data Collection

This protocol will use electronic case report forms (eCRFs) with remote data capture through a qualified third-party vendor. Data entered into the eCRF will correspond to, and be supported by, source documentation maintained at the sites. The investigator is responsible for ensuring that data are properly recorded on each patient's eCRFs and related documents. The data will be entered on the eCRFs in a timely manner and on an ongoing basis. Site data and images will be transferred to Allergan via electronic media.

An IxRS will be used to assign patient identification numbers, randomize patients, and manage study medication inventory. Data will be transferred to Allergan on a periodic basis throughout the study.

7. Statistical Procedures

The primary efficacy analysis will be performed after all patients complete the month 6 visit or discontinue from the study prior to the month 6 visit. The final analysis will be performed after all patients exit the study. There will be separate database locks for the primary analysis and final analysis. Prior to the first database lock a detailed analysis plan (AP) will be approved.

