7.3 Hypothesis and Methods of Analysis

In general, continuous data will be summarized with descriptive statistics (number of patients, mean, standard deviation, median, minimum, and maximum) and will be analyzed using an analysis of variance (ANOVA) model or 2-sample t-test for between-group comparisons and paired t-test for within-group analyses. Categorical variables will be summarized by number of patients, frequency count, and percent, and will be analyzed using Pearson's chi-square or Fisher's exact test (if the expected cell count is less than 5 in 25% or more of the cells). Ordinal variables will be analyzed using the Cochran-Mantel-Haenszel (CMH) test or the Wilcoxon rank-sum test for between-treatment comparisons and the signed-rank test for within-treatment comparisons.

A 2-sided test with a p-value ≤ 0.05 will be considered statistically significant unless otherwise stated.

SAT and Prohibited Treatments Impacting Efficacy Assessment

Usage of SAT or prohibited treatments described below will be considered to impact the efficacy assessments for the visit immediately following the use of SAT or prohibited treatments. The subsequent visits will not be impacted, unless the SAT or prohibited treatments are used again prior to any subsequent visits within the timeframe specified below. The efficacy data that are determined to be impacted by the usage of SAT or prohibited treatment will be considered as missing for the continuous variables with the missing data imputation method described below to be implemented. For the analysis of complete response in ocular symptoms, patients will be analyzed as nonresponders for the visits impacted by SAT or prohibited treatments.

- artificial tears (including SAT): use within 24 hours before each scheduled visit (vehicle run-in visit to month 12 visit)
- lid hygiene: use at least 8 days out of the 30-day window preceding each scheduled visit or any use within 14 days before each office visit
- any use during the study after the randomization visit of oral or topical macrolides, tetracyclines, tetracycline derivative drugs

Missing Data Imputation

ITT analyses of the efficacy variables described below will use the following rules to impute the missing data:

- If the data is missing because the patient discontinued the study due to lack of efficacy or use of SAT or other prohibited treatments that impacts the efficacy assessments,

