7.6 Sample Size Calculation

The total number of patients planned for this study is 527 patients including an estimated 10% attrition rate. The sample size was estimated based on the primary efficacy analysis to compare the proportion of patients with complete overall ocular discomfort response (defined as overall ocular discomfort score equals 0) at Month 6.

Based on the final analysis of an Allergan phase 2 study (protocol 195263-006), the observed proportion of patients with complete overall ocular discomfort response over a 7-day average is 20.0% vs 9.8% (between-group difference of 10.2%) for 0.1% AGN-195263 versus vehicle, respectively. A total of 237 patients per treatment group will achieve 85% power with type I error rate of 0.05 to detect a between-group difference of 10.2% in the proportion of patients with complete overall ocular discomfort response at Month 6. This is based on the two-sided z-test (pooled variance with continuity correction), as implemented in the commercial software, [REDACTED] [REDACTED] [REDACTED] [REDACTED]. Accounting for an anticipated attrition rate of 10%, enrollment of a total of 527 patients at multiple sites is planned.

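### The confidence interval for the primary responder-rate difference names no strata although the CMH test does: a stratified interval, and the CMH continuity correction, should be specified (low severity)

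*Combined protocol and SAP*

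**What the plan says.** - **Randomisation (Section 5.4).** "Patients will be stratified by gender and baseline (day 1) overall ocular discomfort score (1 vs 2 to 3"), which gives the four groups in Table 5.
- **Primary test (Section 7.3.1).** "The null hypothesis will be tested using the CMH method stratified by gender and baseline overall ocular discomfort score (1 vs 2 to 3"). The section does not say whether the CMH statistic is continuity-corrected.
- **Protocol Summary, Efficacy.** "The between-group difference in the proportion of responders will be analyzed using the CMH method stratified by gender and baseline overall ocular discomfort score". Here the stratified method is attached to the difference itself, but no interval is mentioned.
- **Interval (Section 7.3.1, last sentence).** "The between-group difference in the responder rate will be reported with the confidence intervals estimated based on the normal approximation for the binary variable". No stratification, weighting, variance formula or confidence level is given.
- **Decision rule (Section 7.3).** "A 2-sided test with a p-value ≤ 0.05 will be considered statistically significant unless otherwise stated". From this the interval is presumably two-sided 95%.
- **Later detail (opening of Section 7).** "Prior to the first database lock a detailed analysis plan (AP) will be approved". That plan is not among the documents.

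**The concern.** Stratified randomisation balances the arms within each stratum, so variation in response between strata no longer contributes to the error of the treatment difference. The CMH test takes advantage of this. An ordinary two-proportion Wald interval does not: its variance still contains the between-stratum part, so it over-covers when the strata are prognostic.

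Baseline score could well be prognostic. Response means a score of 0 at month 6. A patient entering at 1 needs one grade of improvement, and a patient entering at 3 needs three.

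Two things are at stake, both modest. The main effect estimate could be reported less precisely than the design allows. The CMH p-value could also occasionally fall at or below 0.05 beside a 95% interval that includes 0. A third point is practical: two statisticians following Section 7.3.1 could report different intervals, and the choice should be made before the data are seen.

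**Working it through.** **1. Reproduce the plan's own figure.** Section 7.6 states that "A total of 237 patients per treatment group will achieve 85% power with type I error rate of 0.05", for 20.0% versus 9.8%, using a pooled z-test with continuity correction.
- Mean rate 0.149, so 2 × 0.149 × 0.851 = 0.253598. Sum of arm variances: 0.20 × 0.80 + 0.098 × 0.902 = 0.248396.
- Uncorrected n = (1.960 × √0.253598 + 1.036 × √0.248396)² / 0.102² = 217.3, rounded up to 218.
- Corrected n = (217.3 / 4) × [1 + √(1 + 4 / (217.3 × 0.102))]² = 236.5, rounded up to 237.
- Total: 474 / 0.90 = 526.7, rounded up to 527.

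Both figures reproduce. No strata enter the calculation, so the form of the interval cannot change it.

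**2. Unstratified half-width.** The ITT analysis fills in missing responses, so 527 / 2 = 263.5 per arm is used. Half-width = 1.96 × √(0.248396 / 263.5) = 6.02 points. With 237 per arm it would be 6.35 points.

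**3. Stratified half-width.** Assumptions, none of them in the documents: a share w of patients at score 1, and response at score 1 equal to r times that at 2 to 3 in both arms, with overall rates held at 20.0% and 9.8%. The rate at 2 to 3 is then p / [1 + w(r − 1)]. With equal allocation, the Sato variance term is approximately the unstratified term, minus w(1 − w)(p₁ − p₂)² for each arm, plus w(1 − w)(δ₁ − δ₂)². Here p₁ and p₂ are an arm's rates at score 1 and at 2 to 3, and δ₁ and δ₂ are the risk differences in those two groups.

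With w = 0.30:

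| | r = 2 | r = 3 |
|---|---|---|
| Active, score 1 / 2 to 3 | 30.8% / 15.4% | 37.5% / 12.5% |
| Vehicle, score 1 / 2 to 3 | 15.1% / 7.5% | 18.4% / 6.1% |
| Removed, active + vehicle | 0.00497 + 0.00119 | 0.01313 + 0.00315 |
| Added back | 0.00129 | 0.00341 |
| Sato term | 0.24353 | 0.23553 |
| SE ratio, √(0.248396 / Sato term) | 1.010 | 1.027 |
| Half-width, 1.96 × √(Sato term / 263.5) | 5.96 points | 5.86 points |

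With r = 1 nothing is removed and the ratio is 1.000.

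**4. Simulation.** 60,000 trials per scenario; N = 527; 25% male; 20%, 30% or 40% at score 1; allocation balanced to within one patient per stratum (assumed, as no block size is given). Ranges are over the three shares.

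| | r = 1 | r = 2 | r = 3 |
|---|---|---|---|
| Unstratified SE excess over Sato | 0.0% | 0.9–1.0% | 2.4–2.7% |
| Half-width, unstratified / Sato (points) | 6.0 / 6.0 | 6.0 / 5.9 | 6.0 / 5.8–5.9 |
| Coverage, unstratified | 94.8–95.0% | 95.1–95.2% | 95.5–95.6% |
| Uncorrected CMH p ≤ 0.05, unstratified CI includes 0 | 0.01–0.02% | 0.2% | 0.5–0.7% |

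Sato coverage was 94.8–95.3% over all scenarios run. The crude and Mantel-Haenszel differences differ by only 0.01 to 0.11 percentage points on average.

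**5. Agreement of test and interval, counted in both directions.**
- CMH without continuity correction: the Sato interval disagrees with the test in about 0.1–0.2% of trials.
- CMH with continuity correction, r = 2 and 3: Sato disagrees in about 1.9–2.2% of trials, against 1.0–2.0% for the unstratified interval. The Sato disagreements are cases where the interval excludes 0 and the test is not significant.

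**The case against.** The strongest reply is that nothing is wrong. A stratum-weighted interval is also a normal approximation, the interval sentence directly follows the stratified test, and the Protocol Summary ties the difference to the CMH method. The weights and variance may simply be left to the analysis plan. An unstratified interval would also be defensible: it matches the two-proportion test used for sample size and equals the subtraction of the two reported percentages.

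Most of this stands. A reader might infer that the protocol commits to an unstratified interval. It does not; that is only the plainest reading. A reader might also infer that the primary conclusion is at risk. It is not, because success rests on the CMH p-value.

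A reader might expect a large gain in precision. If response at score 1 were 5 or 8 times that at 2 to 3, the SE excess would be 4.8–6.9% or 7.1–13.0%. The documents neither support nor exclude such ratios. The 8-fold case with 20% at score 1 would need a complete-response rate of about 67% in that group on active treatment (8 × 20.0% / 2.4).

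Finally, a reader might assume that a stratified interval always agrees better with the test. Step 5 shows that this depends on the continuity correction. A corrected CMH test is not far-fetched, since Section 7.6 sizes the trial with a corrected z-test.

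What remains is that the strata used in both randomisation and test are not carried into the interval as written, and a better-matched method is available at no cost.

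**Conclusion.** The point holds as a low-severity improvement. On the plain reading the primary interval is valid, with nominal to slightly conservative coverage, and is a little wider than it needs to be if baseline score predicts response. The SE excess is about 1% at a 2-fold ratio and about 2.5% at 3-fold, which is at most about 0.2 points of half-width around a planned difference of 10.2 points. It is zero if score is not prognostic.

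These sizes rest on assumed stratum shares and response ratios, so no upper bound can be given. The gain in precision applies whichever form of CMH test is used. The gain in agreement between test and interval applies only if the CMH test is not continuity-corrected.

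**What to change.** Before the first database lock, state in Section 7.3.1 and in the analysis plan that:

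- the between-group difference is the Mantel-Haenszel-weighted risk difference over the four randomisation strata, with a two-sided 95% confidence interval using the Sato variance;
- the CMH test is performed without continuity correction.

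Keep the crude percentage per arm as description.

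The cost is a sentence or two in each document, with no new data. The primary test stays a CMH test over the same strata; only its unstated correction is settled. In simulations with 474 patients and equal rates of 9.8% or 15% in both arms, the uncorrected test rejected in 4.9–5.0% of trials. Nothing is lost if the strata are not prognostic.

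If the team prefers a continuity-corrected CMH test, the plan should say so and accept that the Sato interval will disagree with it in about 1–2% of trials, more often than the unstratified interval in most prognostic scenarios. It should also state that the p-value governs.

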7.3.2 Secondary Efficacy Analyses

There are total 8 secondary efficacy variables. Change from baseline in TBUT described in [Section 7.2.2](#) will be analyzed using an analysis of covariance (ANCOVA) model with treatment, gender, and baseline overall ocular discomfort score (1 vs 2 to 3) as factors and the baseline TBUT value as a covariate. The complete blurred vision response, complete corneal sodium fluorescein staining response, and complete ocular burning response will be analyzed using the CMH method stratified by gender and baseline score (1 vs 2 to 3) of the corresponding variable.. In addition, there are 4 secondary efficacy variables derived based on the overall ocular discomfort score. Change from baseline in overall ocular discomfort score will be analyzed by an ANCOVA model with treatment and gender as factors and baseline overall ocular discomfort score as a covariate. The proportion of patients with ≥ 1 -grade improvement from baseline, ≥ 2 grade improvement from baseline and $\geq 50\%$ improvement from baseline in overall ocular discomfort score as defined in [Section 7.2.2](#) will be analyzed by the CMH method stratified by gender and baseline overall ocular discomfort score (1 vs 2 to 3).

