2.2 Clinical Hypotheses

One drop of 0.1% AGN-195263 administered twice daily to each eye:

- Is more effective than vehicle as measured by the proportion of patients with complete overall ocular discomfort response at month 6
- Has an acceptable safety profile throughout the study treatment duration of 12 months

3. Study Design

This is a multicenter, global, randomized, parallel-group, vehicle-controlled study with 6 months of double-masked treatment followed by a 6 month open label treatment extension phase evaluating the safety, efficacy, and systemic pharmacokinetics of 0.1% AGN-195263 in patients with EDE.

Patients will be randomized to receive 0.1% AGN-195263 or its vehicle in a 1:1 ratio. The randomization will be stratified by gender and by baseline (day 1) overall ocular discomfort score (1 vs 2 to 3).

There will be up to 9 study visits including: screening (day -51), standardization (day -21), vehicle run-in (day -14), baseline (randomization, day 1), months 1, 3, 6 (primary and secondary efficacy assessments), 9, and 12/study exit (safety assessments).

The duration of the study for each patient will be up to approximately 14 months.

Use of lid hygiene (ie, warm compress, lid massage, lid scrub) or artificial tears (other than study artificial tears [SAT]) are prohibited from the standardization (day -21) visit until the end of the month 6 visit. Allergan will supply SAT (see Study Procedures Manual for further details). Starting at the standardization (day -21) visit, all eligible patients will administer SAT twice daily in each eye for 6 days. From the vehicle run-in (day -14) visit until the month 6 visit, use of SAT will be considered rescue therapy for intolerable symptoms. After the month 6 visit until the month 12/study exit visit, use of lid hygiene and/or any artificial tear product(s) will be unrestricted.

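### The CMH tests of complete blurred vision, corneal staining and ocular burning response omit baseline discomfort, a randomisation stratum: still valid, but slightly conservative if discomfort is prognostic

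*Combined protocol and SAP*

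**What the plan says.** Section 5.4 defines the randomisation strata by gender and day 1 overall ocular discomfort, 1 against 2 to 3: "There will be 4 stratification groups as shown in Table 5".

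The efficacy analyses then adjust as follows.

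| Month 6 variable | Section | Gender | Baseline discomfort | Own baseline (if not discomfort) |
|---|---|---|---|---|
| Complete discomfort response (primary) | 7.3.1 | yes | yes | not applicable |
| Change in TBUT | 7.3.2 | yes | yes | yes |
| Complete blurred vision response | 7.3.2 | yes | **no** | yes |
| Complete corneal staining response | 7.3.2 | yes | **no** | yes |
| Complete ocular burning response | 7.3.2 | yes | **no** | yes |
| Change in discomfort | 7.3.2 | yes | yes, as a covariate | not applicable |
| Three discomfort improvement responders | 7.3.2 | yes | yes | not applicable |

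For the three bold rows, 7.3.2 says the variable "will be analyzed using the CMH method stratified by gender and baseline score (1 vs 2 to 3) of the corresponding variable". The Protocol Summary (Efficacy) has the same rule: "stratified by gender and baseline value (1 vs 2 to 3) of the corresponding variable". The TBUT model, by contrast, has "treatment, gender, and baseline overall ocular discomfort score (1 vs 2 to 3) as factors and the baseline TBUT value as a covariate". The documents give no reason for the difference.

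**The concern.** When randomisation is balanced within strata, the analysis should normally carry those strata. If a stratification factor predicts the outcome and is left out, the test's variance still includes variation that the balanced allocation has largely removed from the treatment comparison. The test then rejects too seldom under the null and gives away power.

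Discomfort could plausibly predict complete burning or blurred vision response beyond that symptom's own baseline. TBUT is the closest comparator, because it too is not derived from discomfort. There the plan adds the variable's own baseline to the randomisation factors. For the three complete-response variables it substitutes one for the other. At stake is a small amount of power in three of the eight secondary tests, and an unexplained difference in method.

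**Working it through.** **1. The plan's own figure.** Section 7.6 gives 20.0% against 9.8%, two-sided α = 0.05, 85% power, and a pooled z-test with continuity correction.

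- Uncorrected: n = [1.960·√(2·0.149·0.851) + 1.036·√(0.200·0.800 + 0.098·0.902)]² / 0.102² = (0.987 + 0.517)² / 0.010404 ≈ 217.3, so 218 per group.
- Corrected: (217.3/4)·[1 + √(1 + 4/(217.3·0.102))]² ≈ 236.5, so 237 per group.
- With 10% attrition: 474/0.9 = 526.7, so 527.

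The stated 237 and 527 reproduce. They concern the primary variable only. No power is stated for the three secondary variables.

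**2. Why the direction is conservative.** Within one CMH stratum the variance term is n₁n₀m₁m₀/[N²(N−1)], driven by p(1−p). If response probabilities p_d differ by discomfort level d within that stratum, p(1−p) = mean of p_d(1−p_d) + variance of p_d. Stratified allocation balances d between arms within gender. Much of the second term is therefore absent from the real sampling variation, but it stays in the denominator of the test.

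**3. Size, by simulation.** The planned strata (gender × own baseline, 4) were compared with gender × discomfort × own baseline (8). The CMH test had no continuity correction.

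Assumptions not in the documents: N = 474, blocks of 4, 30% men, 40% scoring 1 on each item, own-baseline odds ratio 4, and the primary variable's rates of 9.8% and 20% borrowed for these variables. There were 4000 runs per scenario. The odds ratio is for baseline discomfort 1 against 2 to 3, given own baseline.

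| Correlation of baselines | Discomfort odds ratio | Power, planned (%) | Power, 8 strata (%) | Change (points) |
|---|---|---|---|---|
| 0 | 1 | 89.9 | 89.9 | 0.0 |
| 0 | 3 | 89.9 | 90.3 | +0.4 |
| 0 | 6 | 90.5 | 92.2 | +1.7 |
| 0.4 | 1 | 89.7 | 89.4 | −0.3 |
| 0.4 | 3 | 90.4 | 90.9 | +0.6 |
| 0.4 | 6 | 91.8 | 93.3 | +1.5 |
| 0.7 | 1 | 89.6 | 89.5 | −0.1 |
| 0.7 | 3 | 91.9 | 92.5 | +0.6 |
| 0.7 | 6 | 92.9 | 93.8 | +0.9 |

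Changes are computed before rounding. Null rejection was 4.4% to 5.7% for the planned test and 4.5% to 5.9% with 8 strata (Monte Carlo standard error about 0.35 points). There is no inflation to speak of in either.

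**4. Other assumptions.**

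- N = 474, 30% men, 25% or 40% scoring 1: 0 to −0.4 points at odds ratio 1, +0.3 to +0.6 at 3, +1.1 to +1.7 at 6. Null rejection at odds ratio 6 was 3.7% to 4.8% planned, against 4.4% to 5.6%.
- N = 527, 25% men, 75% scoring 2 to 3, latent correlation 0.6: 89.2→89.0 at odds ratio 2, 82.1→82.8 at 3, 75.6→77.2 at 4, 68.3→70.7 at 6. Null rejection was 4.5% to 5.1% planned, against 4.7% to 5.2%.
- N = 527, blocks of 4, 25% men, 25% scoring 1: −0.3 to 0 at odds ratio 1, +0.1 to +0.2 at 2, +0.8 to +1.3 at 3, +4.5 at 6. Null rejection at odds ratio 6 was 3.5% to 3.9% planned, against 4.4% to 5.0%.

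**5. Sparse strata.** With 25% men, 75% scoring 2 to 3 on both items and latent correlation 0.6, about 11.5% of patients are discordant in each direction. Each discordant male stratum then holds about 527 × 0.25 × 0.115 ≈ 15 men over both arms. At 10% to 20% response that is 1.5 to 3 responders.

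**The case against.** The best defence is that the rule is coherent. All four complete-response tests are stratified by gender and the variable's own baseline, and for the primary variable the own baseline happens to be discomfort. The rule is pre-specified, appears in two places, and uses a sensible prognostic factor. That stands: this is not a slip or a contradiction, and own baseline should stay in the strata. It does not explain why discomfort had to leave, since the TBUT model carries both.

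It is also fair that the gain is modest, rests on assumed inputs, and turns slightly negative when discomfort is not prognostic. The discordant male strata would carry little information. The detailed analysis plan that section 7 promises before the first database lock is not among the documents and may already deal with this.

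Two stronger readings are tempting, and the documents support neither.

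- A reader might infer that these three variables are not analysed by the groups as randomised, or that type I error is inflated. Section 7.1 analyses all efficacy variables in the ITT population by the randomisation schedule. Gender is kept, and the simulations show no inflation.
- A reader might extend the point to the ≥ 1-grade, ≥ 2-grade and ≥ 50% tests and ask for strata 1, 2 and 3, because a pooled 2-to-3 stratum mixes different targets. Those tests already use the randomisation strata, so the argument here does not reach them. The target rationale also fails for ≥ 50%: under the 7.2.2 formula, (1−2)/2 = −50% qualifies from baseline 2, while from baseline 3 a score of 2 gives only −33% and a score of 1 gives −67%. Both baselines need a score of 1 or less.

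**Conclusion.** The point holds as a minor, optional improvement. Three secondary CMH tests omit one of the two randomisation factors, while the nearest comparable analysis keeps both and adds its own baseline. Validity is intact. If discomfort is prognostic beyond own baseline, the planned tests lose power: −0.2 to +1.3 points separated the two analyses at odds ratios of 2 to 3, and about +0.9 to +4.5 points at 6. If it is not prognostic, adding it costs at most about 0.4 points.

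These sizes depend on assumed gender mix, baseline score distribution, correlation, block size, response rates and odds ratios. The direction when discomfort is strongly prognostic was the same under every set of assumptions tried.

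**What to change.** In section 7.3.2 and the matching paragraph of the Protocol Summary, stratify the CMH tests of complete blurred vision, corneal staining and ocular burning response by gender, baseline overall ocular discomfort (1 vs 2 to 3) and the variable's own baseline (1 vs 2 to 3). That makes 8 strata, nested in the four randomisation strata. Carry the same wording into the detailed analysis plan before the first database lock. If the sponsor prefers the present strata, one sentence of justification would be enough.

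The cost is wording only, plus a few sparse male strata, which CMH tolerates. The primary analysis, the other secondary analyses, 237 per group and 527 in total are unchanged.
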